4.4.2.2 Progression-Free Survival

Progression-free survival (PFS) is determined separately on disease status using RECIST v1.1 and modified RECIST, both evaluated by the investigator.

The date of disease progression is derived based on scan/assessment or death dates, not on visit dates. RECIST assessments/scans contributing towards a particular visit may be performed on different dates.

Progression-Free Survival based per RECIST v1.1 assessments:

PFS is defined as date of first occurrence of tumor progression (earliest of the dates of the RECIST component indicating tumor progression) or date of death (in the absence of tumor progression) by any cause or date of censoring, whichever occurs first, minus date of start of study treatment + 1.

For patients not known to have had a tumor progression or died, the date of censoring is the latest date of assessment from their last evaluable RECIST assessment or the date of start of subsequent cancer therapy whichever occurs first. Patients who never received treatment are censored with time equal to 1 day.

If a patient has no evaluable post-screening RECIST assessments, the patient is censored at the day of study treatment initiation unless the patient dies within 18 weeks. In the latter case, the death date will be used as the date of disease progression.

Progression-Free Survival based per modified RECIST assessments:

PFS according to modified RECIST is defined as:

- date of first occurrence of tumor progression after a modified confirmed response if the patient is a responder according to modified RECIST or
- date of first occurrence of tumor progression in case the patient is not a responder according to modified RECIST or
- date of death (in the absence of tumor progression) by any cause or
- date of censoring, whichever occurs first, minus date of start of study treatment + 1.

For patients not known to have had a tumor progression or died after that modified response, the date of censoring is the latest date of assessment from their last evaluable RECIST assessment or the date of start of subsequent cancer therapy whichever occurs first. Patients who never received treatment are censored with time equal to 1 day.

If a patient has no evaluable post-screening RECIST assessments, the patient is censored with time equal to 1 day unless the patient dies within 18 weeks. In the latter case, the death date will be used as the date of disease progression.

The analyses described below are performed separately for PFS based on disease status using RECIST v1.1 and for PFS based on disease status using modified RECIST, both evaluated by the investigator.

Study treatment status at date of disease progression (for patients with disease progression) or at DCO date used for PFS analysis (for patients without disease progression) is summarized. This includes number and percentage of patients who

- were on study treatment at date of disease progression
- discontinued study treatment prior to disease progression
- did not progress and were on study treatment at DCO date
- did not progress and discontinued study treatment.

A KM curve for PFS is presented including the

- number of patients at risk for disease progression (decreasing over time)
- cumulative number of patients with a disease progression (increasing over time)
- cumulative number of patients censored for disease progression (increasing over time) every 6 months time.

Two-sided 95% CIs for PFS probabilities at 6 months time points are added to the KM curve. For calculating these CIs:

- KM estimates are transformed to an unrestricted range by the $\log(-\log(x))$ function
- calculation of CIs by applying normal approximation methods to the transformed scaled
- re-transformation of CIs to the original scale.

This approach is triggered by option CONFTYPE=LOGLOG in SAS PROC LIFETEST.

If applicable, median PFS is estimated together with a two-sided 95% CI according to the method of Brookmeyer and Crowley 1982.

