### **3.3.7 Rationale for the Use of Modified Response Criteria (Immune Based)**

Cancer immunotherapies may result in early apparent radiographic progression (pseudoprogression/tumor immune infiltration), including the appearance of new lesions, followed by delayed response ([Wolchok et al. 2009](#)). Additionally, responding tumors may appear to increase in size because of the influx of immune cells ([Hoos et al. 2010](#); [Pennock et al. 2012](#)). Unconventional response patterns have been described in patients treated with anti-cytotoxic T lymphocyte-associated antigen 4 ([Wolchok et al. 2009](#)) and have been observed in the preliminary experience with atezolizumab in Study PCD4989g. Therefore, modified RECIST will be used in this study to accommodate the possible appearance of new lesions and to allow the apparent increase in tumor burden to be confirmed at a subsequent assessment prior to designation of progressive disease.

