### **3.3.8 Rationale for Allowing Patients to Continue Atezolizumab Treatment Beyond Initial Progression**

Anti-tumor immune responses such as those associated with atezolizumab may result in objective responses that are delayed and that can be preceded by initial apparent radiological progression. This initial apparent progression may occur as a result of either delayed anti-tumor activity and/or robust tumor immune cell infiltration with a concomitant increase in tumor size (pseudo-progression). In addition, lesions that might otherwise be undetectable with conventional imaging may increase in size as a result of these processes and be recorded as new lesions ([Hales et al. 2010](#)).

For example, in IMvigor 210, 121 of the 311 enrolled patients with advanced UC were treated beyond progression for a median of 7.8 weeks (range 0–51 weeks), of whom 20 (17%) subsequently experienced target lesion reduction of at least 30% from their baseline scans ([Rosenberg et al. 2016](#)). Likewise, in Study PCD4989g, several patients with NSCLC who progressed by RECIST v1.1 criteria continued on atezolizumab treatment and demonstrated durable anti-tumor activity. In some responding patients, the growth of known lesions or the appearance of new radiographic lesions were shown to contain immune cells and no viable cancer cells on biopsy.

Because progressive disease (by initial radiographic evaluation) does not necessarily reflect therapeutic failure, conventional response criteria may not adequately assess the activity of immunotherapeutic agents. This study will therefore allow patients to remain on atezolizumab after apparent radiographic progression, provided the benefit-risk ratio is judged to be favorable. Patients should be discontinued for unacceptable toxicity or symptomatic deterioration attributed to disease progression as determined by the investigator after an integrated assessment of radiographic data and clinical status (see Section 4.6.2).

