## **Appendix 2** **Modified Response Evaluation Criteria in Solid Tumors**

Conventional response criteria may not be adequate to characterize the anti-tumor activity of immunotherapeutic agents like atezolizumab, which can produce delayed responses that may be preceded by initial apparent radiological progression, including the appearance of new lesions. Therefore, modified response criteria have been developed that account for the possible appearance of new lesions and allow radiological progression to be confirmed at a subsequent assessment.

Modified Response Evaluation Criteria in Solid Tumors (RECIST) is derived from RECIST, Version 1.1 (RECIST v1.1) conventions and immune-related response criteria (irRC). When not otherwise specified, RECIST v1.1 conventions will apply.

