4.4.2.3 Overall Response

Overall response is determined separately on disease status using RECIST v1.1 and modified RECIST, both evaluated by the investigator.

Best overall response will be derived differently for RECIST assessments and for modified RECIST assessments.

Best overall response based on RECIST v1.1 assessments:

The assessment of best overall response includes post-screening RECIST assessments obtained up to

- disease progression

- death from any cause
- last evaluable RECIST assessment in the absence of disease progression or death
- start of a subsequent anti-cancer therapy

whatever occurs first.

A patient with complete response followed by complete response determined on two consecutive investigator assessments (≥ 4 weeks apart) has confirmed complete response as Best Overall Response.

Otherwise, a patient with complete response followed by partial response or partial response followed by complete response or partial response followed by partial response determined on two consecutive investigator assessments (≥ 4 weeks apart) has confirmed partial response as Best Overall Response.

Otherwise, if there exists at least an assessment of CR, PR or SD, then the patient has Stable disease as Best Overall Response.

If the patient has confirmed complete or partial response, the patient is an overall responder, otherwise, the patient is an overall non-responder. Therefore, if best overall response is Stable Disease, Progressive Disease, Non-Evaluable disease or missing, the patient is an overall non-responder.

Patients who never received treatment are considered as non-responder.

Best overall response based on modified RECIST assessments:

The assessment of best overall response includes post-screening RECIST assessments obtained up to

- death from any cause
- last evaluable RECIST assessment in the absence of death
- start of a subsequent anti-cancer therapy

whatever occurs first.

For best overall response based on modified RECIST, all RECIST assessments are considered even after progression.

The calculations of best overall response based on modified RECIST assessments is similar to the best overall response based on RECIST v1.1 assessments.

In case there are more than one occurrence of CR (or PR in the absence of CR), the first occurrence of CR (respectively PR) will be considered.

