4.4.2.4 Duration of Response

Duration of response (DoR) is determined separately on disease status using RECIST v1.1 and modified RECIST, both evaluated by the investigator

Duration of response based on RECIST v1.1 assessments:

For overall responders, DoR is defined as the time from the date of first occurrence of a confirmed response (CR or PR) to date of tumor progression or death from any cause or to censoring date:

- end of response coincides with the date of tumor progression or death (in the absence of tumor progression) used for the PFS endpoint
- for a patient without disease progression or death following a response, the censored end of response coincides with the PFS censoring date (that is latest RECIST assessment or start of subsequent cancer therapy whichever occurs first)
- DoR is computed as date of PFS event or censoring minus date of first response + 1.

DoR is not defined for overall non-responders.

Duration of response based on modified RECIST assessments:

For overall responders, DoR is defined as the time from the date of first occurrence of a confirmed response (CR or PR) to date of tumor progression following that confirmed response or death from any cause or to censoring date:

- end of response will be the date of tumor progression after that confirmed response or death (in the absence of tumor progression)
- for a patient without disease progression or death following a response, the censored end of response will be the latest RECIST assessment or start of subsequent cancer therapy whichever occurs first.

DoR is not defined for overall non-responders.

Therefore, in case of disease progression followed by a confirmed response of CR or PR (and no confirmed CR or PR before the disease progression), this confirmed response will be considered as Best overall response and the duration of response will start from this confirmed response until next disease progression or death or censoring.

Additionally, a descriptive KM curve (including estimated median) for DoR is provided based on patients with an overall response.

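### Modified-RECIST PFS drops an early progression only if a confirmed response follows at any later time, and counts unconfirmed progression in everyone else

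*SAP*

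**What the plan says.** SAP section 4.4.2.2 has two event rules for PFS by modified RECIST. For a responder the event is the "date of first occurrence of tumor progression after a modified confirmed response if the patient is a responder according to modified RECIST". For anyone else it is the "date of first occurrence of tumor progression in case the patient is not a responder according to modified RECIST". Death and censoring apply to both. Neither rule asks for the progression to be confirmed.

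Responder status comes from SAP section 4.4.2.3: "For best overall response based on modified RECIST, all RECIST assessments are considered even after progression". The window closes only at death, the last evaluable assessment or a new anti-cancer therapy. SAP section 4.4.2.4 follows the same logic: a confirmed response after a progression becomes the best overall response, and the next progression ends it.

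The protocol (section 2.2) defines PFS once for both sets of criteria, as time to first progression or death, with no split by response. Section 3.3.7 says that modified RECIST is used to accommodate new lesions and "to allow the apparent increase in tumor burden to be confirmed at a subsequent assessment prior to designation of progressive disease". The introduction to Appendix 2 repeats that the criteria "allow radiological progression to be confirmed at a subsequent assessment", but the rules in that appendix make confirmation permissive. SAP section 4.4.4 plans no sensitivity analysis.

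**The concern.** Whether a progression scan is an event should be settled by that scan, or by a fixed confirmation step soon after it. Here it depends on whether a response is confirmed at any later time. A patient who later responds cannot have a progression event before that response. A patient whose disease merely stabilises after the same scan has the event at once, even if the next scan does not confirm it.

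Response is thereby built into PFS. A subgroup with more late responses gains PFS mechanically, and the SAP reports this endpoint with Kaplan-Meier curves, medians and many subgroup displays, including by PD-L1 expression. The resulting curve is neither time to first progression nor time to confirmed progression, so a reader cannot place it beside either.

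**Working it through.** **Inputs.** Event rules and responder window: SAP sections 4.4.2.2 and 4.4.2.3. Scan schedule: Protocol Appendix 1, every 9 weeks to week 54, then every 12 weeks. Confirmation: Appendix 2, a consecutive assessment at least 4 weeks later showing a further measurable increase. Counts: Protocol section 3.3.8, where 121 of 311 patients were treated beyond progression, "of whom 20 (17%) subsequently experienced target lesion reduction of at least 30% from their baseline scans".

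**Step 1: the plan's own figure.** 20/121 = 16.5%, which rounds to the stated 17%.

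**Step 2: the rules applied to worked sequences.** All four patients have SD at week 9 and PD at week 18.

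| After week 18 | First PD for all | SAP rule | Confirmed PD for all |
|---|---|---|---|
| A: PR, PR, onward | event, week 18 | censored, week 54 | censored, week 54 |
| B: SD to week 54 | event, week 18 | event, week 18 | censored, week 54 |
| C: confirmed growth | event, week 18 | event, week 18 | event, week 18 |
| D: PR not confirmed, then SD | event, week 18 | event, week 18 | censored, week 54 |

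A and B are identical to week 18, and in neither is the increase confirmed. The first-PD and confirmed-PD rules each treat them alike. Only the SAP rule separates them.

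**Step 3: a bound on the upward shift.** Let T1 be time to first PD or death, TS the event time under the SAP rule, and p the share of patients with PD followed by a confirmed response. TS = T1 for everyone outside that share, so

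S_SAP(t) − S_first(t) = P(T1 ≤ t < TS) ≤ p.

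The gap reaches p only when all those early PDs have occurred and none of these patients has progressed again.

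**Step 4: a guide to p.** 20/311 = 6.4% (exact 95% CI 4.0% to 9.8%), or about 64 per 1000 patients. A further 121 − 20 = 101 patients (101/311 = 32.5%) were treated beyond progression without such a reduction. Under the SAP rule the first PD of a non-responder counts whether or not it is confirmed.

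**Step 5: simulation under assumptions.** 100,000 patients per scenario, protocol scan schedule, p = 6.4%. The true median PFS, the share with PD then SD, and the durations after early progression are assumed. PFS at 26 weeks:

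| Median PFS (months) | PD then SD | First PD | SAP | Confirmed PD | SAP − first | SAP − confirmed |
|---|---|---|---|---|---|---|
| 2 | 0% | 23.7% | 30.1% | 30.1% | +6.4 | 0 |
| 2 | 10% | 23.8% | 30.1% | 38.3% | +6.3 | −8.2 |
| 4 | 0% | 48.7% | 55.0% | 55.0% | +6.3 | 0 |
| 4 | 10% | 48.8% | 55.2% | 63.6% | +6.4 | −8.4 |
| 6 | 0% | 62.0% | 68.4% | 68.4% | +6.4 | 0 |
| 6 | 10% | 61.8% | 68.2% | 76.6% | +6.4 | −8.4 |

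With p = 2% the 26-week shift against first PD is about 2 points (25.8 − 23.8 = 2.0, median 2 months). With p = 10% it is about 10 (33.7 − 23.8 = 9.9). By week 52, with p = 6.4% and no PD-then-SD patients, it falls to about 4 points (7.0 − 2.8 = 4.2; 20.9 − 16.7 = 4.2; 34.8 − 30.4 = 4.4), because some of these patients have progressed again. Simulated medians jump between scan dates and are not used.

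**The case against.** The strongest defence is coherence. Appendix 2 lets a patient reach a best response of PR or CR even after confirmed progression. The SAP's best-response and duration-of-response rules follow that, and the PFS rule matches them. The non-responder branch also agrees with the protocol's first-occurrence definition. This explains the rule, but it does not stop PFS status from depending on later response.

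A reader might infer that the protocol requires every progression to be confirmed and that the SAP breaches this. The documents do not support that: section 3.3.7 speaks of allowing confirmation, and Appendix 2 makes it optional. The clearer departure is the responder branch against the PFS definition in section 2.2.

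A reader might also infer that the SAP estimate is simply inflated. That holds only against a first-PD rule.

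Nor is 6.4% an estimate of the affected share. The protocol does not say that those 20 patients had progression by modified RECIST, under which new lesions alone and non-target growth are not progression. It also does not say that their lesion reduction was a confirmed response.

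Finally, a confirmation rule also looks ahead. It does, but by one scheduled assessment and in the same way for every patient, whereas the SAP rule has no fixed limit.

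**Conclusion.** The concern holds. The SAP's modified-RECIST PFS is conditional on later response, departs from the protocol's definition in responders, and leaves the optional confirmation step unused in everyone else.

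Against first PD for all, the upward shift cannot exceed the share with PD then confirmed response: 6.4 points on the prior-study upper guide, and about 2 to 10 points at 26 weeks if that share is 2% to 10%. Against a confirmed-PD rule, with the share at 6.4%, the SAP estimate was equal or up to about 8.4 points lower at 26 weeks when 0% to 10% of patients have PD then SD. That direction assumes that the early PD of later responders is not confirmed at the next scan; patients with confirmed PD and then response would pull the other way.

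The existence of the problem follows from the SAP text alone. Only its size depends on assumptions. The consequence is limited: this is one of two versions of a secondary endpoint in a descriptive single-arm safety study, and no primary conclusion rests on it.

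**What to change.** Apply one rule to every patient, whatever the later response:

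- The event is the first PD confirmed at the next consecutive assessment at least 4 weeks later, by Appendix 2's criterion of a further measurable increase, dated at the first PD. Death remains an event.
- An unconfirmed PD counts as an event if no further evaluable scan exists, or if death or new anti-cancer therapy comes before the next scan.
- Report first PD for all (the literal protocol definition) and the current SAP rule as sensitivity analyses.
- State in the SAP that confirmation, optional in Appendix 2, is required for this endpoint.

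The cost is SAP text and reprogramming on collected data. Protocol section 4.6.2 keeps patients who stop treatment for progression under tumor assessment, and Appendix 1 schedules scans until confirmed progression. Some patients will still lack a confirmatory scan, hence the second item. A patient with confirmed PD and then a response will have a PFS event before the duration of response starts; a table footnote should say so. SAP version 3.0 is dated December 2022, in an open-label study, so the change should be labelled as late and the current rule kept visible. If the sponsor retains the current rule as the main analysis, it should justify it, label it as response-dependent and show both alternatives.

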4.4.2.3 Overall Response

Overall response is determined separately on disease status using RECIST v1.1 and modified RECIST, both evaluated by the investigator.

Best overall response will be derived differently for RECIST assessments and for modified RECIST assessments.

Best overall response based on RECIST v1.1 assessments:

The assessment of best overall response includes post-screening RECIST assessments obtained up to

- disease progression

- death from any cause
- last evaluable RECIST assessment in the absence of disease progression or death
- start of a subsequent anti-cancer therapy

whatever occurs first.

A patient with complete response followed by complete response determined on two consecutive investigator assessments (≥ 4 weeks apart) has confirmed complete response as Best Overall Response.

Otherwise, a patient with complete response followed by partial response or partial response followed by complete response or partial response followed by partial response determined on two consecutive investigator assessments (≥ 4 weeks apart) has confirmed partial response as Best Overall Response.

Otherwise, if there exists at least an assessment of CR, PR or SD, then the patient has Stable disease as Best Overall Response.

If the patient has confirmed complete or partial response, the patient is an overall responder, otherwise, the patient is an overall non-responder. Therefore, if best overall response is Stable Disease, Progressive Disease, Non-Evaluable disease or missing, the patient is an overall non-responder.

Patients who never received treatment are considered as non-responder.

Best overall response based on modified RECIST assessments:

The assessment of best overall response includes post-screening RECIST assessments obtained up to

- death from any cause
- last evaluable RECIST assessment in the absence of death
- start of a subsequent anti-cancer therapy

whatever occurs first.

For best overall response based on modified RECIST, all RECIST assessments are considered even after progression.

The calculations of best overall response based on modified RECIST assessments is similar to the best overall response based on RECIST v1.1 assessments.

In case there are more than one occurrence of CR (or PR in the absence of CR), the first occurrence of CR (respectively PR) will be considered.

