### **4.4.1 Permitted Therapy**

Patients who experience infusion-associated symptoms may be treated symptomatically with acetaminophen, ibuprofen, diphenhydramine and/or famotidine or another H2 receptor antagonist, as per standard practice (equivalent medications may be substituted per local practice). Serious infusion-associated events manifested by dyspnea, hypotension, wheezing, bronchospasm, tachycardia, reduced oxygen saturation or respiratory distress should be managed with supportive therapies as clinically indicated (e.g., supplemental oxygen and  $\beta$ 2-adrenergic agonists; see [Appendix 6](#)).

Systemic corticosteroids and tumor necrosis factor- $\alpha$  inhibitors may attenuate potential beneficial immunologic effects of treatment with atezolizumab, but may be administered at the discretion of the treating physician after consultation with the Medical Monitor (see Exclusion Criterion 21 [Section [4.1.2](#)]). If feasible, alternatives to corticosteroids should be considered. Premedication may be administered for cycles  $\geq 2$  at the discretion of the treating physician after consultation with the Medical Monitor. The use of inhaled corticosteroids for COPD and mineralocorticoids (e.g., fludrocortisone) and low-dose corticosteroids for patients with orthostatic hypotension or adrenocortical insufficiency is

allowed. Megestrol administered as an appetite stimulant is acceptable while the patient is enrolled in the study.

Colony-stimulating factors, such as granulocyte colony-stimulating factor and erythropoietin, should only be used according to manufacturers' labels and the ASCO and ASCO/ASH guidelines ([Smith et al. 2006](#); [Rizzo et al. 2010](#)).

*Inactivated vaccinations (such as influenza, COVID-19) are permitted. Live, attenuated vaccines are not permitted (see Section 4.4.2).*

*Patients experiencing a mixed response requiring local therapy for control of three or fewer lesions may still be eligible to continue study treatment at the investigator's discretion. The Medical Monitor is available to advise as needed. Patients who receive local therapy directed at a target lesion will no longer be evaluable for radiographic response but will remain evaluable for progression.*

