#### **4.4.2 Prohibited Therapy**

Any concomitant therapy intended for the treatment of cancer, whether health authority-approved or experimental, is prohibited. This includes but is not limited to the following:

- Chemotherapy, hormonal therapy, immunotherapy, radiotherapy, or investigational agents (except for maintenance therapies outlined in Section 4.1.1 and 4.1.2)
  - After completion of Cycle 1, certain forms of radiotherapy may be considered for palliation if patients are deriving benefit (e.g., treatment of known bone metastases or symptomatic hematuria)
- Traditional herbal medicines are not recommended because the ingredients of many herbal medicines are not fully studied, and their use may result in unanticipated drug-drug interactions that may cause or confound assessment of toxicity
- Patients who are receiving a receptor activator of nuclear factor kappa B ligand inhibitor (denosumab) prior to enrollment must be willing and eligible to receive a bisphosphonate instead while on study; denosumab could potentially alter the activity and the safety of atezolizumab
- Patients should not receive abatacept or belatacept treatment (those who were receiving it must stop it > 8 weeks before study entry)

Live, attenuated vaccines (e.g., FluMist®) are prohibited within 4 weeks prior to initiation of study treatment, during atezolizumab treatment, and for 5 months after the discontinuation of atezolizumab.

Patients are not allowed to receive immunostimulatory agents, including but not limited to interferon (IFN)- $\alpha$ , IFN- $\gamma$ , or IL-2, during the entire study. These agents, in combination with atezolizumab, could potentially increase the risk for autoimmune conditions.

With the exception of autoimmune disease patients, patients should not receive immunosuppressive medications, including but not limited to cyclophosphamide, azathioprine, methotrexate, and thalidomide. These agents could potentially alter the activity and the safety of atezolizumab.

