### **Appendix 3**

### **Response Evaluation Criteria in Solid Tumors:**

### **Excerpt from Original Publication (cont.)**

Patients with a global deterioration of health status requiring discontinuation of treatment without objective evidence of disease progression at that time should be reported as “symptomatic deterioration.” Every effort should be made to document objective progression even after discontinuation of treatment. Symptomatic deterioration is not a descriptor of an objective response; it is a reason for stopping study therapy. The objective response status of such patients is to be determined by evaluation of target and nontarget disease as shown in [Table 1](#), [Table 2](#), and [Table 3](#).

For equivocal findings of progression (e.g., very small and uncertain new lesions; cystic changes or necrosis in existing lesions), treatment may continue until the next scheduled assessment. If at the next scheduled assessment progression is confirmed, the date of progression should be the earlier date when progression was suspected.

In studies for which patients with advanced disease are eligible (i.e., primary disease still or partially present), the primary tumor should also be captured as a target or nontarget lesion, as appropriate. This is to avoid an incorrect assessment of complete response if the primary tumor is still present but not evaluated as a target or nontarget lesion.

## Appendix 4

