4.6.5 Concomitant medications

Subsequent anti-cancer therapies will be summarized overall and by type of anti-cancer therapy on the Safety Population.

By-patient listings including site and patient identifier will be provided for each of the following type of therapies based on the Safety Population:

- Concomitant Medications (separately for corticosteroids, immunosuppressive medications and any other medications)
- On-study Surgery and Procedure (Non-Cancer)
- On-Study Cancer Radiotherapy
- On-Study Tumor Surgery data.
- Subsequent anti-cancer therapies

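### SAP 4.4.2.3 does not carry out the protocol rule that a patient whose target lesion is treated locally is no longer evaluable for response

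*SAP*

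**What the plan says.** **Protocol.** Section 4.4.1 says that patients with a mixed response "requiring local therapy for control of three or fewer lesions may still be eligible to continue study treatment at the investigator's discretion". It then sets an evaluability rule: "Patients who receive local therapy directed at a target lesion will no longer be evaluable for radiographic response but will remain evaluable for progression". Section 4.4.2 adds a second route to on-study local treatment: "After completion of Cycle 1, certain forms of radiotherapy may be considered for palliation if patients are deriving benefit". The examples given there are known bone metastases and symptomatic hematuria. Appendix 3 says that, where the primary is still present, "the primary tumor should also be captured as a target or nontarget lesion, as appropriate", so an irradiated primary may be a target lesion.

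**SAP.** Section 4.4.2.3 derives best overall response as follows: "The assessment of best overall response includes post-screening RECIST assessments obtained up to" the earliest of a short list of stops. For RECIST v1.1 these are progression, death, the last evaluable assessment, and "start of a subsequent anti-cancer therapy". For modified RECIST the list is the same without progression, and the section confirms that scans after progression count. Section 4.4.2.5 (disease control) repeats the same response derivation, and section 4.4.2.4 (duration of response) starts its clock at the responses so derived. Section 4.4.4 plans no sensitivity analysis. Section 4.7 covers only dates of death and missing AE grades.

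**The concern.** The protocol draws a distinction that the analysis has to carry out: after local therapy to a target lesion, scans still count for progression but no longer for response. The SAP does not draw it. Followed as written, its window admits every later investigator assessment until one of the listed stops. Shrinkage produced by radiotherapy or surgery could then be counted as a response to atezolizumab.

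ORR, DCR, DoR and PFS under both criteria are named secondary endpoints (protocol 2.2). The trial has one arm, so no control group would show the same misattribution.

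**Working it through.** No stated sample size, power or interval is in question, so the check is a comparison of texts, with small sums to show how a response could arise.

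**1. Does an existing stop cover local therapy?**

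- *Subsequent anti-cancer therapy.* The SAP does not define the term. However, SAP 4.6.5 lists "On-Study Cancer Radiotherapy" and on-study tumour surgery as items separate from subsequent anti-cancer therapies. Protocol 4.6.2 ends study treatment for another systemic anti-cancer therapy, whereas the local therapy of protocol 4.4.1 is given while atezolizumab continues. The natural reading is that local therapy is not a subsequent therapy.
- *Last evaluable assessment.* The same phrase sets the PFS censoring date in SAP 4.4.2.2. Because these patients stay evaluable for progression, their later scans remain evaluable in that sense. The SAP has no separate term for evaluable for response.

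Neither stop carries out the protocol rule.

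**2. How a response could arise without prior progression (both criteria).** The lesion sizes are hypothetical.

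- Baseline: 30 + 30 = 60 mm.
- Week 9: 34 + 24 = 58 mm. Change = (58 − 60)/60 = −3.3%, so SD.
- The 34 mm lesion is irradiated or removed and then reads 0 to 15 mm. The sum is 24 to 39 mm. Change = (24 − 60)/60 = −60% to (39 − 60)/60 = −35%.
- Scheduled scans are 9 weeks apart in the first 54 weeks (Appendix 1), so two consecutive ones meet the SAP's requirement of at least 4 weeks. If the investigator enters PR at both, SAP 4.4.2.3 gives a confirmed PR. Under protocol 4.4.1 the patient has no evaluable response after the procedure.

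**3. How it could arise after progression (modified RECIST only).**

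- The progression threshold from a 60 mm nadir is 60 × 1.20 = 72 mm. One lesion stays at 30 mm and the other grows to 72 − 30 = 42 mm, an absolute rise of 12 mm, above the required 5 mm. This is PD.
- The PR threshold is 60 × 0.70 = 42 mm. If the grown lesion is treated and then reads 42 − 30 = 12 mm or less, the sum qualifies as PR.
- Under RECIST v1.1 the window closed at the PD, so nothing changes. Under modified RECIST, two PR entries make a responder. SAP 4.4.2.2 then takes progression after the confirmed response as the PFS event, in place of the earlier PD, and SAP 4.4.2.4 starts a DoR.

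**4. Direction by endpoint.**

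- *ORR:* adding scans at the end of a patient's sequence cannot undo a confirmed response already reached, so the count can only rise.
- *DCR:* it changes only for a patient with no earlier CR, PR or SD. The patient in step 2 already counts through the week 9 SD.
- *DoR:* the direction is not fixed, since it depends on how long the added responses last.
- *PFS, modified RECIST:* an earlier progression can be replaced by a later one.

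**5. Scale for ORR.** Each wrongly counted responder adds 100/n percentage points, which is 0.1 at n = 1000 (planned size, protocol 6.1). As a reference take 15%, the overall ORR that protocol 1.3.3 quotes from the earlier phase II study (IMvigor 210). The numbers added are assumed; the documents give none.

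| Added responders (assumed) | ORR | Clopper-Pearson 95% CI |
|---|---|---|
| 0 | 150/1000 = 15.0% | 12.8% to 17.4% |
| 5 | 155/1000 = 15.5% | 13.3% to 17.9% |
| 10 | 160/1000 = 16.0% | 13.8% to 18.4% |
| 30 | 180/1000 = 18.0% | 15.7% to 20.5% |

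**The case against.** The strongest reply is that the SAP measures no tumours. It takes the investigator's timepoint responses and treats a best response of non-evaluable as non-response. An investigator who applies protocol 4.4.1 would enter no CR or PR after treating a target lesion, and the SAP would then add no responder. This stands in part. A false response needs CR or PR entered on two scans contrary to the protocol. But neither document tells sites to enter NE after local therapy, and the SAP has no check if they do not.

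The second reply concerns size, and most of it stands.

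- The mixed-response paragraph is in italics, which the protocol's amendment rationale says marks substantive new information in version 15. SAP section 1 dates that version 17 December 2021. The version 9 synopsis attached to the SAP lacks the paragraph.
- Version 1 is dated July 2016. Protocol 3.2 gives about 6 years in total with 48 months after the last enrolment, leaving about 2 years for accrual. If enrolment kept to that plan, version 15 came roughly three years after the last patient entered. Actual dates are not given.
- Median treatment in IMvigor 210 was 12 weeks (protocol 1.3.4). Few patients would still have been on treatment without a response.
- Palliative radiotherapy was already allowed in version 9, so exposure does not begin with version 15. But it often involves non-target sites: blastic bone lesions are nonmeasurable, and a primary tumour may be recorded as nontarget.

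The version history may explain the gap but does not close it, because the SAP names version 15 among the protocols on which it is based.

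A third reply is that these are secondary endpoints of a descriptive study with no formal hypothesis. That is right, and it limits the priority of the point.

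**Conclusion.** SAP 4.4.2.3, and the DoR and DCR sections that rely on it, do not implement the protocol's non-evaluability rule. Applied literally, the SAP would count an investigator-entered CR or PR that the protocol disallows. ORR can only be raised. Under modified RECIST, DoR and PFS can also be affected.

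The size is unknown and probably small: 0.1 percentage point of ORR per affected patient at n = 1000, with an unknown number of patients. The 5 to 30 patients in the table are an illustration, not an estimate. Added responders up to 10 would leave ORR (16.0%) within the interval around 15%. The primary safety endpoint is unaffected. The change should be made, but nothing in the main safety conclusions depends on it.

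A reader might infer three stronger things, none of which the documents support:

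- *That the SAP overrides the protocol and actively scores local shrinkage as response.* It is silent, and the false response depends on what the investigator enters.
- *That ORR is inflated by a definite amount, for example by applying 1% to 3% to all 1000 patients.* No rate is given, and the late appearance of the mixed-response provision argues against so broad a base.
- *That ORR, DCR and DoR are all biased upward.* Only the ORR count has a fixed direction.

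**What to change.** In SAP 4.4.2.3, 4.4.2.4 and 4.4.2.5, for both RECIST v1.1 and modified RECIST, add: assessments after on-study radiotherapy, surgery or other local therapy to a target lesion are not used to establish or upgrade a response, and remain in use for progression. Make clear that confirming an earlier unconfirmed CR or PR counts as establishing it.

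Keep these patients in the denominator with their best response before the procedure. Protocol 4.4.1 does not specify this, so the SAP should state it as its own choice. Identify the patients by matching the on-study radiotherapy and tumour-surgery records listed in SAP 4.6.5 to the site of the target lesion, and report how many are affected. If there are none or very few, that count settles the matter.

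The cost is a few lines of SAP text, one derived flag and some matching work, since neither document says that those records identify the lesion treated. ORR may come out slightly lower.
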